7.10 Concomitant Therapy

Permitted Therapy

Subjects are permitted to use topical, ocular, intra-articular, intranasal, and inhalational corticosteroids (with minimal systemic absorption). Physiologic replacement doses of systemic corticosteroids are permitted, even if > 10 mg/day prednisone equivalents. A brief course of corticosteroids for prophylaxis (eg, contrast dye allergy) or for treatment of non-autoimmune conditions (eg, delayed-type hypersensitivity reaction caused by contact allergen) is permitted.

8.0 STATISTICAL CONSIDERATIONS

8.1 Objectives

Primary Objective:

To compare the 12-month rate of progression-free survival (PFS) achieved with the combination of nivolumab, a programmed death (PD-1) inhibitor, and radiation therapy in localized/locally advanced urothelial cancer patients, who are ineligible for chemotherapy, to a historical control reference 12-month PFS rate.

Secondary Objectives:

- 1) To assess the toxicity of concurrent nivolumab and radiation therapy in urothelial cancer.
- 2) To determine overall response rate (ORR).
- 3) To determine metastasis-free survival (MFS).
- 4) To determine overall survival (OS).
- 5) To evaluate the quality of life (QOL) and bladder functioning during and after

the therapy.

- 6) To explore the relationships of PD-1 expression, PDL-1 expression, and the Th1/Th2 cytokine ratio to clinical outcomes (response, PFS, MFS, and OS).

8.2 Endpoints

8.2.1 The primary endpoint (PFS) is defined in Section 4.9.

8.2.2 The secondary endpoints are defined in the following protocol sections:

Toxicity assessment is defined in Section 5, and toxicity-evaluable patients are defined in Section 4.7.

Response is defined in Section 4.5, and response-evaluable patients are defined in Section 4.6.

MFS and OS are defined in Sections 4.8 and 4.10, respectively.

QoL and bladder functioning questionnaires (FACT-BI and BISI) are specified in Section 7.3 and shown in Appendix E.

PDL-1 (and other biomarkers) are listed in Section 7.2, and will be assessed by IHC (or other assay methods).

8.3 Design

This is a 1-arm 1-stage survival type design focused on the primary endpoint of the 12-month PFS rate. The study design assumptions are:

- 1) A population reference value of 50% 12-month PFS rate from standard of care with RT alone (from Supplementary Appendix Figure 1(a) in reference [4]);
- 2) A hypothesized 75% 12-month PFS rate for patients treated with Nivolumab+RT;
- 3) Exponentially distributed PFS times;
- 4) Accrual time of 24 months;
- 5) An additional follow-up time of 12 months for all patients;
- 6) Significance level alpha = 0.025 (1-sided, due to the directional hypothesis);
- 7) Power = 0.95 (high due to the unmet need for improved therapy options for study eligible patients).

Under these 7 assumptions, the study will require N=30 evaluable patients, as calculated using the “One Arm Survival” program on the www.crab.org website. Evaluable for

PFS and toxicity evaluable (see Section 4.7) have the same definition: registered and having started Nivolumab therapy. Allowing for up to 10% of enrolled patients who may become inevaluable, up to 34 patients may need to be enrolled.

8.4 Analysis

8.4.1 For the Primary Objective, the censored PFS distribution will be summarized with the Kaplan-Meier (K-M) survivorship estimate. A graph of the K-M curve for PFS will be generated along with the Hall-Wellner 95% confidence band, and a display of the number of patients at risk at several time points, below the X-axis. Summary statistics (12-month PFS rate, median PFS, etc.) will be calculated from the K-M life table, each one with its respective 95% confidence interval (CI). To test whether the point estimate of the 12-month PFS rate is statistically significantly greater than the assumed historical reference value of 0.50, the point estimate will be compared to the upper critical value of 0.64 obtained from the “One Arm Survival” program mentioned in Section 8.3.

8.4.2 For Secondary Objective (1) toxicity rates will be estimated among the toxicity evaluable patients (defined in Section 4.7). Frequency distributions of each toxicity type by severity grade will be generated. For a given grade(s), the point estimate of the toxicity rate will be computed, along with its 95% (Wilson type) CI.

8.4.3 For Secondary Objective (2), the ORR will be estimated among the response evaluable patients (defined in Section 4.6), and among all patients. Frequency distributions of best response will be generated for each of those sets of patients. The point estimate of the ORR will be computed, along with its 95% (Wilson type) CI.

8.4.4 For Secondary Objectives (3) and (4), summary statistics of MFS and OS will be calculated from their respective K-M life tables in the similar fashion as described in Section 8.4.1 for OS. K-M graphs of the censored MFS and OS distributions will also be generated.

8.4.5 For Secondary Objective (5), the QOL data will be used to test the following hypotheses:

1. Demographics and clinical variables (age, sex, race/ethnicity) will be related to length of time on trial (i.e., days or weeks);
2. Demographic and clinical variables (cancer stage, performance status, number of comorbidities) will be related to: (a) average levels of QOL; and (b) variability in QOL over the course of the trial.

We will use a linear mixed-effects model to test the association between baseline patient factors (demographic and clinical measures) and QOL. The model will have a random intercept, slope, and leading coefficient for the measurement of QOL across all 15 time points identified in the Study Calendar, Section 2.3. The patient factors will be used as predictors of QOL with baseline QOL as a covariate. The association will be investigated based on the statistical testing for each of the slope and intercept fixed-effects using a Wald test. As the measurements on each individual would be correlated, the first-order autoregressive AR(1) residual will be used for the residual variance-covariance structure. We will also investigate other variance-covariance residual structures to further improve the model fitting. The final model will be selected based on the Akaike information criterion (AIC).

8.4.6 For Secondary Objective (6), the tissue markers (e.g., PD-1, PDL-1, TILs) and serum marker Th1/Th2 cytokine ratio first will be summarized descriptively. The categorical markers PD-1 and PDL-1 will be summarized via frequency distributions (over their IHC expression categories of 0, 1+, 2+, and 3+). The continuous markers (e.g., TILs, Th1/Th2 cytokine ratio, etc.) will be summarized with standard descriptive statistics. These descriptive analyses of the tissue and plasma biomarkers will be performed for each time point at which the each marker is determined.

Response (CR/PR vs not) will be modeled as a function of a dichotomized version of prestudy PD-1 and PDL-1 expression (separately) using exact logistic regression. Similar logistic model analyses of those tissue markers determined at other time points prior to response determination will also be performed. Similar modeling will be performed for the continuous (ungrouped) markers (e.g., TILs from tissue, and the Th1/Th2 cytokine ratio). The statistical goal of these exploratory analyses is to obtain the point and 95% CI

estimates of the odds ratio (OR), and to simply determine the direction and approximate magnitude of these associations for use in planning a subsequent study.

Censored PFS will be modeled as a function of a dichotomized version of prestudy PD-1 and PDL-1 expression (separately) using Cox proportional hazards (PH) regression. Time-dependent Cox model analyses of those tissue markers determined at all time points will also be performed. A similar Cox modeling strategy will be used for the continuous (ungrouped) markers (e.g., TILs from tissue, and the Th1/Th2 cytokine ratio from serum). For all Cox models, the PH assumption will be examined graphically by inspection of log(-log) survival plots, and of Epanechnikov kernel-smoothed hazard functions. Non-PH for a given marker variable will be incorporated into the Cox model by including a (ln(PFS) * marker) interaction term in the Cox model. The statistical goal of these exploratory analyses is to obtain the point and 95% CI estimates of the hazard ratio (HR), and to simply determine the direction and approximate magnitude of these associations for use in planning a subsequent study.

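### The 0.64 cut-off for 12-month PFS fits an exponential-model estimate but is applied to a Kaplan-Meier estimate, so at N=30 the rule has about 5% one-sided alpha and 89% power, not 2.5% and 95%

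*Combined protocol and SAP*

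**What the plan says.** Section 8.3 sizes a one-arm, one-stage trial with the One Arm Survival program. Its assumptions include:

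- "A population reference value of 50% 12-month PFS rate from standard of care with RT alone"
- "A hypothesized 75% 12-month PFS rate for patients treated with Nivolumab+RT"
- "Exponentially distributed PFS times"
- "Accrual time of 24 months", plus 12 further months of follow-up for every patient
- "Significance level alpha = 0.025 (1-sided, due to the directional hypothesis")
- "Power = 0.95 (high due to the unmet need for improved therapy options for study eligible patients")

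The result is 30 evaluable patients, with up to 34 enrolled.

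On the analysis side, Section 8.4.1 states: "Summary statistics (12-month PFS rate, median PFS, etc.) will be calculated from the K-M life table", each with a 95% confidence interval. For the test against 0.50, "the point estimate will be compared to the upper critical value of 0.64 obtained from the" same program. No exponential-model estimate of the 12-month rate is planned, so the statistic compared with 0.64 is the K-M estimate. The plan gives no error rates for that comparison other than those in Section 8.3.

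**The concern.** A critical value holds its alpha only for the statistic it was derived for. An exponential estimate of the 12-month rate draws on all events and all person-time, here up to 36 months. The K-M value at month 12 uses only what happens up to month 12, so its standard error is larger. A cut-off set for the more precise statistic is too lenient for the less precise one.

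This is the trial's only formal decision rule for its primary objective. If the pairing is wrong, the chance of declaring an inactive regimen superior to the historical rate is higher than stated, and the power is lower. The plan can also report a significant result beside a 95% interval that contains the null value.

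**Working it through.** **Inputs (Section 8.3).** S0(12) = 0.50, S1(12) = 0.75, exponential PFS, accrual 24 months, follow-up 12 months, one-sided alpha 0.025, power 0.95, N = 30. Uniform accrual is my assumption.

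**Step 1: reproduce N = 30 and 0.64.**

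- Hazards: λ0 = ln 2/12 = 0.05776 and λ1 = −ln(0.75)/12 = 0.02397 per month.
- Probability of an observed event: p = 1 − (e^(−12λ) − e^(−36λ))/(24λ), which is 0.729 under the null and 0.430 under the alternative. Expected events in 30 patients are 21.9 and 12.9.
- On the cube-root scale, the standard error of λ̂^(1/3) is about λ^(1/3)/(3√events). With λ0^(1/3) = 0.3866 and λ1^(1/3) = 0.2883:
  - N = {[1.960 × 0.3866/√0.729 + 1.645 × 0.2883/√0.430] / [3 × (0.3866 − 0.2883)]}² = 29.9, so 30.
  - Critical hazard = {0.3866 × [1 − 1.960/(3√21.9)]}³ = 0.0368, so critical S(12) = e^(−12 × 0.0368) = 0.643.

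Both of the plan's figures are recovered. The log-hazard scale also gives N = 30 (29.8) with a cut-off of 0.634. The untransformed scale gives 32.5 and 0.668.

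**Step 2: error rates of the rule as written.** With every patient followed for 12 months, the K-M estimate is X/30, where X is the number progression-free at 12 months. Since 19/30 = 0.633 fails and 20/30 = 0.667 passes, the rule is X ≥ 20:

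- alpha = P(X ≥ 20 | 30, 0.50) = 0.0494
- power = P(X ≥ 20 | 30, 0.75) = 0.894

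The null standard error is √(0.25/30) = 0.091. A 2.5% cut-off is therefore 0.50 + 1.96 × 0.091 = 0.68 by normal approximation, or 21/30 = 0.70 exactly. For X ≥ 21, alpha is 0.0214 and power 0.803.

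**Step 3: simulation (200,000 trials, n = 30, no early loss).**

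| Statistic compared with 0.64 | Alpha | Power |
|---|---|---|
| Exponential estimate, exp(−12 × events/person-time) | 0.024 | 0.955 |
| K-M at 12 months | 0.049 | 0.896 |

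The same cut-off meets the stated design with one estimator and misses it with the other.

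**Step 4: sensitivity of the K-M rule.**

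| Situation | Alpha | Power |
|---|---|---|
| n = 29 (≥ 19), exact | 0.068 | 0.914 |
| n = 31 (≥ 20), exact | 0.075 | 0.936 |
| n = 32 (≥ 21), exact | 0.055 | 0.920 |
| n = 33 (≥ 22), exact | 0.040 | 0.901 |
| n = 34 (≥ 22), exact | 0.061 | 0.939 |
| n = 30, 5% lost by month 12, simulated | 0.061 | 0.906 |
| n = 30, 10% lost, simulated | 0.068 | 0.907 |
| n = 30, 20% lost, simulated | 0.077 | 0.900 |

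The loss rates are assumptions; the documents give none. Some early censoring is plausible: Section 4.9 counts only deaths from urothelial cancer as events, and eligibility selects for comorbidity.

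**Step 5: agreement with the interval.** At 20/30 the log-log standard error is √[(1 − 0.667)/(30 × 0.667)]/|ln 0.667| = 0.318. The 95% limits are 0.667^exp(±1.96 × 0.318), that is 0.469 to 0.805. The Wilson interval is 0.488 to 0.808. Both include 0.50. At 21/30 the log-log lower limit is 0.503.

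**The case against.** The arithmetic for n = 30 with complete follow-up is not in dispute. The strongest points on the other side are these.

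- **One scenario.** The 5% and 89% figures belong to n = 30 with nobody censored early. At n = 33 alpha is 0.040, 1.6 times nominal rather than double. At n = 34 power is 0.939, only about one point short. This stands as a qualification, but every case examined has alpha above 0.025 and power below 0.95.
- **The source of 0.64 is inferred.** The program's internals are not in the documents. True, although the exponential assumption and the match to both N and cut-off are strong evidence. The error rates of the K-M rule are binomial facts whatever the program does.
- **Five per cent is tolerable in phase II.** It may be, if declared. The plan declares 2.5%, and power would still be 0.89 at N = 30.
- **The clash with the interval is narrow.** With n = 30 and full follow-up it arises only at 20/30, and Section 8.4.1 does not name the interval method for the 12-month rate. That is fair, but 20/30 is exactly the result at which the rule first declares success.
- **The exponential estimate could be tested instead.** It keeps N = 30 and 0.64. However, progression is largely found at scheduled procedures (week 13 and months 6, 9 and 12). When events are recorded only at three-monthly assessments, that test's simulated alpha rises to about 0.066.

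**Conclusion.** The concern holds. The cut-off of 0.64 delivers the stated alpha and power for an exponential-model estimate, but the plan applies it to a K-M estimate. At the design's own N = 30 with full 12-month follow-up, the rule has exact one-sided alpha 0.049, about twice the stated value, and power 0.894, about 6 points below the stated value. Across 29 to 34 evaluable patients, or with 5% to 20% assumed early loss at n = 30, alpha lies between about 0.04 and 0.08 and power between about 0.89 and 0.94. The simulated figures assume exponential PFS and uniform accrual. The exact figures need only the two 12-month rates and complete follow-up to month 12. Because this is the sole test of the primary objective, it should be corrected before analysis.

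**What to change.** **Recommended.** In Section 8.4.1, replace the comparison with 0.64 by this rule: success is declared if the lower limit of the two-sided 95% log-log confidence interval for the K-M 12-month PFS rate exceeds 0.50. With 30 patients and no early censoring this means at least 21/30. In Section 8.3, restate the attained one-sided alpha as about 0.021 and power as about 0.80 for N = 30, and say that these assume complete follow-up. Under assumed losses of 5%, 10% and 20% by month 12, simulated power falls to about 0.75, 0.72 and 0.68, with alpha about 0.015. If all 34 are evaluable, the rule needs 24/34 (alpha 0.012, power 0.789).

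This costs a wording change in two sections and no extra patients, but it gives up the 0.95 power that the plan chose deliberately.

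**Alternatives to weigh openly.**

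- Keep N = 30, 0.64 and the stated error rates, and make the exponential-model 12-month estimate the test statistic. This is less attractive because of its sensitivity to scheduled assessment.
- Keep K-M with alpha at most 0.025 and power at least 0.95. The smallest exact design is 49 evaluable patients with at least 32 progression-free (alpha 0.022, power 0.954), which is 19 more than planned.

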2.3 Study Calendar

Prestudy labs, physical exam and EKG should be done within 28 days of day 1. Day 1 labs can be done within 3 days of day 1. A window of +/- 3 days is permitted for the days of nivolumab therapy.

Testing	Pre study	Wk 1	Wk 3	Wk 5	Wk 7	Wk 9	Wk 11	Wk 13	Wks 15,17, 19,21, 23,25	6, 9 and 12 mths ⁴
H and P	X	X	X	X	X	X	X	X	X	X
VS, Wt	X	X	X	X	X	X	X	X	X	X
PS	X	X	X	X	X	X	X	X	X	X
Tox	X	X	X	X	X	X	X	X	X	X
Labs ¹	X	X	X	X	X	X	X	X	X	X
TSH, free T3/T4	X				X			X		X
ECG ²	X									
Cystoscopy ⁷	X							X		X

Biopsy ⁷	X							X		X
CT/MRI ³ of abdomen/pelvis	X							X		X
CXR/ chest CT ³	X									
Nivolumab		X	X	X	X	X	X	X	X	
visits during RT ⁵		X	X	X	X	X				
PFS/OS ⁶		X	X	X	X	X	X	X	X	X
Biomarkers ³	X				X			X		X
QOL questionnaires ³	X	X	X	X	X	X	X	X	X	X

1. Labs include: CBC diff, platelets, Electrolytes, BUN, creatinine, glucose, Albumin, alkaline phosphatase, total bilirubin, calcium, total protein, SGOT, SGPT. Pregnancy test for women of child bearing potential within 7 days of study enrollment and every 6 weeks thereafter.
2. ECG at screening and repeat if clinically indicated.
3. ICF, Baseline biomarkers, QOL questionnaires and all tumor evaluation/measurement scans must be within 42 days prior to treatment. CT/MRI of abdomen and pelvis is required for pretreatment and subsequent tumor assessments. CXR/CT chest is required at screening only to evaluate for metastases. Biomarkers should be collected at time of PD.
4. 6, 9 and 12 month visits will be from start of therapy. A window of +/- 28 days is permitted for these visits.
5. RT will be done **continuously** daily Monday to Friday (except for weekends and holidays) for a total of 32-35 fractions from week 1 to week 8. The time period of 8 weeks is a maximum duration as the radiation fractions can get delayed due to holidays, machine downtime, patient cancellation due to transportation etc. During RT patients should be evaluated for toxicity at a minimum every other week. Nivolumab should be started +/- 3 days of first day of RT.

6. After 12 months the patients will be followed for PFS and OS every 3 months for a maximum of 5 years.

7. Screening cystoscopy and biopsy can be performed within 6 months of day 1. On study cystoscopy will be done at week 13 and at months 6, 9 and 12 +/- 28 days. Biopsies will be required at week 13, month 6 and month 12 +/- 28 days. Month 9 biopsies done if clinically indicated.

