6.4 Quality of Life (QOL) Questionnaires [Appendix F]

The QOL questionnaire will be administered at the 15 time points listed in the header of the Study Calendar in Section 2.3. The FACIT symptom index score for cancer and specific bladder symptom index questionnaires will be completed at a maximum of 15 timepoints starting with pre-therapy, the days of nivolumab therapy, and then 6 and 12 month timepoints. The change in score indices will be analyzed by repeated measures analysis and modeling and will be reported.

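### Section 8.4.5 uses pre-therapy QOL as both a response and a covariate, so its intercept test addresses QOL level given baseline rather than the average level named in hypothesis 2(a)

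*Combined protocol and SAP*

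**What the plan says.** Section 8.4.5 (protocol Section 8.4, Secondary Objective 5) sets out the only model specified for QOL.

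- **Hypothesis.** Hypothesis 2 says that stage, performance status and number of comorbidities "will be related to: (a) average levels of QOL; and (b) variability in QOL over the course of the trial". This point concerns part (a).
- **Response.** The mixed model has random terms "for the measurement of QOL across all 15 time points identified in the Study Calendar, Section 2.3".
- **Covariate.** "The patient factors will be used as predictors of QOL with baseline QOL as a covariate".
- **Test.** "The association will be investigated based on the statistical testing for each of the slope and intercept fixed-effects using a Wald test".

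Two other places settle whether the pre-therapy score is among the responses. Section 6.4 has the questionnaires "completed at a maximum of 15 timepoints starting with pre-therapy, the days of nivolumab therapy, and then 6 and 12 month timepoints". The Section 2.3 calendar marks QOL in the pre-study column, and its footnote 3 gives the timing: "ICF, Baseline biomarkers, QOL questionnaires and all tumor evaluation/measurement scans must be within 42 days prior to treatment". No sentence takes the pre-therapy row out of the response.

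**The concern.** There are two linked problems.

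First, one measurement stands on both sides of the equation. For the pre-therapy row the model predicts a score from itself, which pushes the baseline coefficient up.

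Second, hypothesis 2(a) is about level, with no qualifier such as given baseline or change from baseline. The factors it names exist before treatment, and Section 8.4.5 itself treats them as baseline factors. Whatever part of their effect is already visible before treatment is carried by the pre-therapy score, and holding that score fixed takes that part out of the intercept term. That term is one of the two on which the Wald tests rest.

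With about 30 patients, a level effect that has been shrunk in this way could be reported as no association when the model was in fact answering a different question.

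**Working it through.** **Inputs.** From the documents: 15 stated time points, the pre-therapy score among them, baseline QOL as a covariate, and 30 evaluable patients. Not in the documents: any QOL standard deviation, any baseline-to-later correlation ρ, or any expected factor effect. All values of these below are assumptions, with ρ run from 0.2 to 0.9.

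**Step 1: the stated count of 15.** It does not reproduce.

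- Calendar header: 1 pre-study + 13 dosing visits (weeks 1, 3, …, 25) + 3 (months 6, 9, 12) = 17.
- Section 6.4 list: 1 + 13 + 2 (months 6 and 12) = 16.
- The Section 6.4 list gives 15 if week 25 and month 6 count as one visit. It also gives 15 if pre-therapy is dropped, but that contradicts Section 6.4's own statement that the list starts there.

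**Step 2: share of a constant level difference removed.** Let a factor shift every score, baseline included, by d. Assume equal variances and a common correlation ρ. The within-group coefficient of a patient's mean over 15 rows on the baseline score is

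b = Cov(mean, Y₀)/Var(Y₀) = (1 + 14ρ)/15.

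The adjusted factor effect is d − b·d = d(1 − b), so b is the share removed. With post-baseline rows only, b = ρ.

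| ρ (assumed) | Share removed, 15 rows | Share removed, post-baseline rows only |
|---|---|---|
| 0.2 | (1+2.8)/15 = 25% | 20% |
| 0.5 | (1+7.0)/15 = 53% | 50% |
| 0.7 | (1+9.8)/15 = 72% | 70% |
| 0.9 | (1+12.6)/15 = 91% | 90% |

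Setting b = 0.5 gives ρ = (7.5 − 1)/14 = 0.46. With 17 rows it is (8.5 − 1)/16 = 0.47, so the count mismatch hardly matters here.

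**Step 3: check by simulation.** Generalised least squares, 6,000 simulated patients, 15 visits, true constant effect 1.0:

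| Mean baseline-to-later correlation | All rows, no covariate | All rows, with covariate | Post-baseline rows, with covariate |
|---|---|---|---|
| 0.41 | 1.00 | 0.54 | 0.58 |
| 0.55 | 1.02 | 0.42 | 0.45 |
| 0.67 | 0.95 | 0.29 | 0.31 |
| 0.54 (random slope added) | 0.97 | 0.36 | 0.40 |

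Without the covariate the effect is recovered in full. With it, the loss follows the formula: at 0.55 the formula gives (1+7.7)/15 = 0.58 and the fitted coefficient was 0.583. The formula is approximate once a random slope is added: at 0.54 it gives 0.57, against a fitted 0.62. The factor-by-time slope did not change with adjustment. Most of the shrinkage comes from the covariate itself; the duplicated row adds a few percentage points.

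On a QOL-like scale (30 patients, 17 visits, random-intercept SD 10, slope SD 6, AR(1) residual SD 7, all assumed), a constant 8-point difference was estimated as 2.1 to 2.3 points with the covariate and 7.9 without it.

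**Step 4: an effect that arises only after baseline.** With the same assumed SDs and a 6-point shift from the first post-baseline visit:

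- All rows: intercept 4.6 to 5.2 and slope 1.1 to 2.6 points per year across repeated simulations. Runs made with and without the covariate gave the same slope.
- Post-baseline rows with the covariate: intercept 5.9 to 6.1, and slope between −0.7 and 0.4 against a true value of zero. The Monte Carlo standard error of the slope was about 0.4 in the run of 120 trials.

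The covariate does nothing here because the factor is unrelated to the baseline score. The distortion comes from drawing a straight line through a step when the pre-therapy row is a response.

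**The case against.** Baseline adjustment is routine, and QOL during follow-up given starting QOL is a legitimate quantity. Section 8.4.5 also words its general aim broadly, as association between baseline factors and QOL. This stands in part. A reader might infer that the model cannot answer 2(a). The fairer statement is that it answers a conditional question, while 2(a) as worded asks an unconditional one, and the plan does not say which is meant.

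A reader might also infer that adjustment removes most of the effect. The documents do not support that. They give no correlation, and the effect could act through tolerance of treatment rather than be present at the start, in which case the covariate would leave it in place.

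A third tempting reading is that using baseline twice creates a false slope. Step 4 shows otherwise: the slope is the same without the covariate. Its effect on the Wald test was also small in the 120-trial run, where the slope was significant in 8% of trials as written and 5% with post-baseline rows only.

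It could be argued that the 15 points were meant as the 13 dosing visits plus months 6 and 12, all post-baseline. Section 6.4 rules this out, since it counts pre-therapy first.

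Finally, the simulations used simplified models. The plan also names a leading coefficient among the random terms, and it allows other residual structures chosen by AIC. The simulated point values are therefore illustrations. The direction of the shrinkage does not depend on them.

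**Conclusion.** The concern holds in a limited form. The text makes the pre-therapy score both a response and a covariate, and the covariate turns the intercept test into a test of level given baseline, which is not what 2(a) states.

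The size is conditional. If the factor effect is fully present at baseline and constant over time, between 25% and 91% of it is removed for ρ from 0.2 to 0.9, and more than half only above about 0.46. If the effect starts after baseline, the covariate removes none of it. The pre-therapy response row then lowers the intercept estimate and induces a slope under a linear time trend, with or without the covariate.

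This is a secondary objective with no QOL sample size or decision rule. The primary 12-month PFS test is not affected.

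**What to change.** Amend Section 8.4.5 to name the model for each hypothesis.

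1. **Hypothesis 2(a), average level:** fit the mixed model to all visits, with pre-therapy as a response row and no baseline QOL covariate. Do not read this model's slope as change after baseline, because the step artefact remains in it.
2. **Change after baseline, including slope effects:** use post-baseline rows only as responses, with baseline QOL as a covariate.
3. If level given baseline is what 2(a) was meant to ask, reword 2(a) to say so and use the second model for it.
4. Reconcile the 15 time points with the calendar header (17) and the Section 6.4 list (16), and list the response rows explicitly.

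The cost is a few sentences in the plan and one extra model fit. No new data are needed.
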